#### Blood sample analysis

- Liquid chromatography–mass spectrometry (LC-MS) will be run when samples for all the patients (10) are collected.

#### Statistical Analysis

- Pharmacokinetic parameters (Area under curve, half life, Tmax and Cmax) of simvastatin and simvastatin acid before and after bariatric surgery will be calculated for each subject using pharmacokinetics software. (See Pharmacokinetics Evaluation Form) Each patient will serve as their own control and pharmacokinetic parameters before and after LSG will be compared with appropriate statistical tests (student t-test if parametric, mann-whitney u test if non-parametric).

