## **Aims & Objectives**

The aim of the study is to investigate the effect of laparoscopic sleeve gastrectomy on the pharmacokinetics of simvastatin.

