## Study Procedure

- Patient recruitment
  - o Subject selection:
    - Inclusion criteria:
      - Planned for laparoscopic sleeve gastrectomy at National University Hospital
      - Taking simvastatin
      - Aged 21 or above
    - Exclusion criteria:
      - Patient on concomitant treatment with medications/ food/ herbal supplements that may affect the pharmacokinetics of simvastatin: boceprevir, conivaptan, cyclosporine, efavirenz, mitotane, tocilizumab, rifamycin, amiodarone, amlodipine, aprepitant, azithromycin, colchicine, fenofibrate, imatinib, raltegravir, ranolazine, teriflunomide, ticagrelor, fusidic acid, protease inhibitors, telaprevir, telithromycin, gemfibrozil, erythromycin, clarithromycin, carbamazepine, rifampicin, ketoconazole, fluconazole, itraconazole, voriconazole, diltiazem, verapamil, dexamethasone, prednisolone, phenytoin, ritonavir, indinavir, nelfinavir, bosentan, telithromycin, nefazodone, St John's wort, orlistat, sibutramine and other strong CYP 3A4 inhibitors/ inducers
      - Pregnant ladies
  - o All patients referred to the National University Hospital for laparoscopic sleeve gastrectomy will be screened for inclusion into the study. Potential subjects will be screened and assessed at the Bariatric Surgery Clinic. Written consent will be taken at the Clinic. ( See Patient consent form) The potential subject's permission to be referred into a study will be obtained by the attending healthcare professionals prior to direct contact by any member of the research team, and the subject's agreement will be documented. The study aims to recruit 10 patients.
  - o Patients will be asked to stop taking simvastatin 5 days before the day of the study. Fasting is not required. Patients will also be informed that they will obtain SGD \$100 after completing the study as a token of appreciation and to compensate their time and inconvenience (if the study subject fails to complete the study, compensation will be pro-rated and paid out as \$50 per each blood sampling session).
  - Training
    - o Study members, namely [name], [name], [name], will be trained for the following: 1) Explaining procedure of the study to recruited study subjects after informed consent is taken; 2) Delivering blood sample from the bariatric clinic to the lab for storage and 3) Procedures for compensating the patient after the study

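### Eight before/after comparisons are planned with no primary comparison, alpha or multiplicity rule, so the result that decides can be chosen after the data are seen

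*Combined protocol and SAP*

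**What the plan says.** The aim is general: to "investigate the effect of laparoscopic sleeve gastrectomy on the pharmacokinetics of simvastatin". Aims & Objectives singles out no parameter or analyte.

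The Statistical Analysis section lists what will be derived for each patient: "Pharmacokinetic parameters (Area under curve, half life, Tmax and Cmax) of simvastatin and simvastatin acid before and after bariatric surgery". It then says: "Each patient will serve as their own control and pharmacokinetic parameters before and after LSG will be compared with appropriate statistical tests". The tests named are "student t-test if parametric, mann-whitney u test if non-parametric". The word paired does not appear. The own-control wording implies it, but Mann-Whitney U is a test for independent samples.

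The Abstract comes nearest to a main quantity. It presents the study as one of systemic exposure after sleeve gastrectomy, and it postulates a fall in the bioavailability of simvastatin. It also describes the drug as being hydrolysed in the stomach to its active form. None of this is carried into the Statistical Analysis section as an endpoint.

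On size, the Study Procedure section says "The study aims to recruit 10 patients". No sample size calculation, alpha, multiplicity rule or decision rule appears in the documents. On timing, the Blood sample analysis section says that LC-MS "will be run when samples for all the patients (10) are collected".

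**The concern.** Four parameters for each of two analytes make eight comparisons of equal standing. Nothing fixes in advance which of them answers the aim, so the headline comparison can be picked once all eight p-values are known. A p-value picked that way does not carry the error rate of a single pre-named test.

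The choice of analyte matters as much as the choice of parameter. On the Abstract's own mechanism, less gastric hydrolysis could lower the acid while the parent stays level or rises. That is an inference from the Abstract and not a statement in it. In that event the plan gives no rule for which analyte bears on the question.

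The stake is what the study can be used for. The Abstract says that existing advice to choose an alternative to simvastatin after bariatric surgery rests mainly on theory. A result offered as evidence on that advice should rest on a comparison named beforehand.

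**Working it through.** There is no stated error rate, alpha or power to reproduce. The check asks how often at least one of the eight tests would be significant if surgery changed nothing.

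**Inputs from the documents**
- Comparisons: 4 parameters × 2 analytes = 8 (Statistical Analysis).
- Patients: 10, each measured before and after surgery (Study Procedure; Statistical Analysis).

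**Inputs assumed, because the documents do not give them**
- Two-sided 0.05 for each test.
- Any one significant result is read as an effect.
- Correlation among the eight before/after differences: 0 to 0.9.
- Correlation between a patient's before and after values: 0 to 0.7. This matters only if the tests are run unpaired.

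**Independent tests.** 1 − (1 − 0.05)^8 = 1 − 0.6634 = 33.7%.

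**Correlated tests, paired.** The simulation used 40,000 trials for each setting, n = 10, eight normally distributed parameters with no true change, and paired t-tests on 9 degrees of freedom.

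| Common correlation | At least one p < 0.05 |
|---|---|
| 0 | 33.6% |
| 0.2 | 32.3% |
| 0.3 | 30.9% |
| 0.4 | 28.4% |
| 0.5 | 26.1% |
| 0.6 | 23.7% |
| 0.7 | 20.7% |
| 0.8 | 17.1% |
| 0.9 | 12.9% |

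Each single test stayed at about 5%. Patterns closer to pharmacokinetic data (AUC with Cmax 0.7-0.9, parent with acid 0.3-0.8, other pairs within an analyte 0-0.3) gave 24% to 31%.

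**The same data, tests run unpaired.** With common correlation 0.5, the chance of at least one p < 0.05 depends strongly on the before/after correlation.

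| Before/after correlation | At least one p < 0.05 |
|---|---|
| 0 | 25.6% |
| 0.3 | 13.3% |
| 0.5 | 6.4% |
| 0.7 | 1.4% |

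The fall comes from ignoring the pairing. At before/after correlation 0.7 each single test rejects only 0.2% of the time, which is a loss of power and not a control of multiplicity.

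**Smaller families**
- AUC alone, both analytes, independent: 1 − 0.95^2 = 9.75%.
- A false decrease in either AUC, independent: 1 − 0.975^2 = 4.9%.
- One pre-named comparison: 5%.
- Bonferroni over eight, 0.05/8 = 0.00625 each: 1 − (1 − 0.00625)^8 = 4.9% if independent, and at most 5% under any dependence.

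**Limits.** The range covers the correlations tried and is not a bound. Treating all eight parameters as normal is an idealisation, above all for Tmax, which can take only the scheduled post-dose times of 1, 2, 3, 5 and 7 h. Rank tests were not simulated.

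**The case against.** The strongest reply is that this is a ten-patient, single-centre pharmacokinetic study with no claim attached to a p-value. The aim is to investigate an effect, and estimating the parameters meets it whether or not any of them changes. The four parameters are standard, and reporting parent and acid side by side is informative even if they diverge. The Abstract's emphasis on exposure and its expected direction also narrow the question. If claims are confined to AUC, the figure is at most 9.75% for two independent tests, and 4.9% for a false decrease.

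Much of this stands. A reader might infer that the plan promises a 5% error rate and breaks it, or that it produces a false finding in a fixed share of trials such as one in four. The documents support neither reading. They give no alpha and do not say that one significant result out of eight establishes an effect. They imply pairing without stating it, and they give no correlations from which a single figure could be derived. A reader might also take the reporting of both analytes as a fault in itself, and it is not.

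What does not stand is the view that the Abstract settles the matter. Exposure suggests AUC, but no parameter, analyte or test is tied to it. The expected fall is in the bioavailability of simvastatin, while the concern about efficacy concerns the active form. The documents nowhere call the study exploratory, and they do plan significance tests on every parameter. The lower rates under unpaired testing are no defence, because they are bought with power and sit badly with patients acting as their own controls.

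**Conclusion.** The point holds as a gap in the specification. Eight comparisons are planned, and nothing says which one decides, at what level, or how the other seven are to be read.

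Its size is conditional. With paired tests, an assumed two-sided 0.05 for each, and any significant result read as an effect of surgery, the chance of at least one false positive is about 13% (common correlation 0.9) to 34% (independence). Unpaired tests would give a different and often lower rate, down to about 1% in the settings tried. The number shows what the missing rule allows and is not a property that the plan states.

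This is an inexpensive improvement worth making. It does not invalidate the design or the data to be collected.

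**What to change.** Before the LC-MS run, amend the Statistical Analysis section to say:

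- One comparison decides: the within-patient before/after change in AUC over 0-7 h for one analyte, chosen by the sponsor with a reason given. Simvastatin acid is one example, since the Abstract calls it the active form. The parent drug could also be argued for from the postulated fall in simvastatin bioavailability.
- That comparison uses a paired test at two-sided 5%, reported with its estimate and confidence interval.
- The other seven comparisons are secondary. They are reported as estimates with confidence intervals and no claim of significance, or they are Holm-adjusted.
- If Holm is used, the seven are tested only when the deciding comparison is significant. The first step is then 0.05/7 = 0.0071. Without that condition, the deciding test and the adjusted seven could together reach 5% + 5% = 10%.

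The cost is a few sentences, with no extra patients, samples or assays. By the plan's own schedule no concentrations exist until all samples are in, so the choice can still be made blind to the results. The downside is small: a change in a secondary parameter alone could no longer be headlined as a demonstrated effect of surgery.

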## **Study design**

Study design: prospective, open, non-randomized, controlled, single-centre study

The study will be conducted with the approval from the Institutional Ethics and Research Board.

Participants: 10 patients undergoing sleeve gastrectomy

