    - o Nurses of the bariatric clinic will be trained to administer the study according to the study protocol: 1) Making sure study subject is suitable for blood sampling e.g. has stopped simvastatin for 5 days, vitals stable, IV plug properly set by physician; 2) Monitoring self-administration of simvastatin by the patient; 3) Drawing blood according to the pre-set time points; 4) Monitoring patient for vitals and comfort after blood draw; 5) Documentation of details of blood sampling on the "Record for Blood Sampling"
    - o The training details (i.e. date, name of trainee and trainer, contents of training) will be recorded. Training records will be kept for 3 years after completion of the study.
  - Pre-bariatric surgery

- Recruited subjects will come to the clinic at 8:30am on the day of study. Blood taking will start at 9:30am. Fasting is not required.
- Nurses at the Bariatric Surgery Clinic will set an IV plug for blood sampling. They will also confirm with the subjects that simvastatin has been stopped for 5 days. Nurses will also check that patient has not been taking the interacting drugs in the past 5 days. The subject will take simvastatin 20mg at 9:30am (0 h). 5 mL of blood will be sampled at 0 h, 1 h, 2 h, 3 h, 5 h, 7 h. Blood sample will be taken in EDTA tubes and kept in ice. (See Record of blood sampling). Study subjects will be staying at the Bariatric Surgery Clinic and monitored by nurses who are trained for care and monitoring of patients with IV cannulation.
- All the blood samples will be transferred to the lab in ice after the last blood sample is drawn at 7 h. Blood samples will be spun down and frozen.
- Surgical procedure
  - Laparoscopic sleeve gastrectomy (LSG) is performed for most patients requiring bariatric surgery at the National University Hospital. This is a restrictive procedure where the stomach is tubularized and the excess part is removed. About 75% of the stomach will be removed in this way.
- Post-bariatric surgery
  - Patients will be invited to return to the clinic for another blood sampling session after 3 months. If the patient takes proton pump inhibitor prior to the study, the same dose should be maintained at 3 months when the patient returns for the study.
  - The blood sampling procedure for pre-bariatric surgery will be repeated.
  - \$100 will be given to patient upon completion of the second blood sampling session.

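### The non-parametric test named for the before/after comparison (Mann-Whitney U) is for independent groups, and the t-test is not stated to be paired

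*Combined protocol and SAP*

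**What the plan says.** The Study design section describes a single group: "Participants: 10 patients undergoing sleeve gastrectomy". The study is labelled controlled, but no separate control group is described. Under Study Procedure, the same patients return 3 months after surgery and "The blood sampling procedure for pre-bariatric surgery will be repeated".

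The Statistical Analysis section lists AUC, half-life, Tmax and Cmax for simvastatin and simvastatin acid. It then says "Each patient will serve as their own control and pharmacokinetic parameters before and after LSG will be compared", and the same sentence gives the method: "compared with appropriate statistical tests (student t-test if parametric, mann-whitney u test if non-parametric". No paired test is named anywhere in the document, and there is no criterion for choosing between the two branches.

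Two other places matter. The sampling schedule reads "5 mL of blood will be sampled at 0 h, 1 h, 2 h, 3 h, 5 h, 7 h". The recruitment text allows for patients who attend only one session: "if the study subject fails to complete the study, compensation will be pro-rated".

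**The concern.** The sentence sets up a within-patient comparison and then names a between-group test for it. Mann-Whitney ranks all 20 values together and ignores which two belong to the same patient, so between-patient variation, which the own-control design is meant to remove, stays in the comparison. The t-test branch is different: the name used covers both the paired and the independent form, so that branch is unspecified rather than wrong.

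The non-parametric branch is likely to be used. With the stated sampling times, observed Tmax can take only five post-dose values (1, 2, 3, 5 and 7 h), and with 10 patients a skewed AUC or Cmax could be sent there too.

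The Abstract postulates a fall in bioavailability. A test that discards the pairing makes it more likely that a real fall is reported as no change. The choice of test also decides who is analysed: an unpaired test would accept values from a patient with one session, and a paired test cannot.

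**Working it through.** **The plan's own figure.** There is none to reproduce. The document gives no alpha, power, effect size, CV or within-patient correlation, and no basis for the sample size.

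**Inputs from the document.** 10 patients, each measured twice (Study design; Study Procedure); tests as named in Statistical Analysis.

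**Assumed inputs.** Two-sided 5%; log-normal exposure; total CV 50% or 70%; correlation of log values 0 to 0.90; a fall of 30% or 50%.

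**Why pairing matters.** The SD of log exposure is σ = √ln(1 + CV²). For CV 70%, σ = √ln(1.49) = 0.63. The SD of a within-patient log difference is σ√(2(1 − ρ)):

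- ρ = 0: 0.63 × √2 = 0.89
- ρ = 0.50: 0.63 × √1 = 0.63
- ρ = 0.78: 0.63 × √0.44 = 0.42

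A 30% fall is ln(0.7) = −0.357. As a multiple of those SDs it is 0.40, 0.56 and 0.85. A paired test gains from that increase. An unpaired test judges the shift against the between-patient spread whatever ρ is.

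**Simulation.** 10 pairs, 40,000 replicates per scenario, exact critical values (Mann-Whitney U ≤ 23, signed-rank W ≤ 8, and their mirror images). Entries are power for Mann-Whitney vs signed-rank on log values; the last column is the Mann-Whitney type I error.

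| Correlation | CV 70%, 30% fall | CV 70%, 50% fall | CV 50%, 30% fall | Type I error |
|---|---|---|---|---|
| 0 | 19% vs 20% | 59% vs 57% | 32% vs 32% | about 4% |
| 0.28 | 17% vs 26% | 60% vs 71% | 30% vs 42% | 2% |
| 0.50 | 14% vs 34% | 63% vs 85% | 28% vs 55% | 0.9% |
| 0.78 | 10% vs 65% | 68% vs 99% | 26% vs 88% | 0.1% |

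The signed-rank type I error stays near 5% throughout. At correlation 0.90 (CV 70%), power is 8% vs 93% for a 30% fall and 72% vs 100% for a 50% fall.

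**Check under a different set-up.** Normal data with a shift of 1 between-patient SD and 10,000 runs:

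| Correlation | Mann-Whitney vs signed-rank | Independent vs paired t |
|---|---|---|
| 0 | 51% vs 50% | 56% vs 51% |
| 0.5 | 52% vs 78% | 58% vs 79% |
| 0.7 | 55% vs 94% | 61% vs 95% |

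The pattern is the same, and it shows what is at stake if the t-test were also run unpaired.

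**Tmax.** A simulation on the 1, 2, 3, 5, 7 h grid, with ties and an assumed shift, gave 49% vs 68% at correlation 0.5 and about equal power at 0. Read this as direction only.

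**Scale.** With between/within CV of 60%/30%, paired t-test power on log values vs raw differences is 68% vs 54% (30% fall) and 93% vs 82% (40% fall). For the signed-rank test it is 66% vs 62% and 92% vs 89%. The log scale matters mainly for the t-test.

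**The case against.** The strongest reply is that the harm is conditional and conservative. The size rests wholly on assumed values. At correlation 0 nothing is lost, and correlation may be low: the Abstract cites individual changes in atorvastatin exposure after gastric bypass that ran from a threefold fall to a twofold rise. For a 50% fall most of the power survives, and false positives are not inflated. For a 30% fall at CV 70% and correlation up to 0.50, even the signed-rank test reaches only 20% to 34%, so the test is not the only limit on a 10-patient study. All of this stands. It bears on how much is lost, not on whether the named test fits the design.

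The wording about own control and appropriate tests could also be taken to show that a paired analysis was intended. That is fair for the t-test. It does not help the other branch, because the parenthesis says which tests are meant and Mann-Whitney has no paired form.

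A third point is that the main figures are for continuous exposure, whereas Tmax is the clearest reason to expect the non-parametric branch. The power figures in the main table do not carry over to Tmax, but the grid-based check shows the same direction of loss.

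Finally, the payment rule shows only that dropout is foreseen, not how those data would be analysed. That is so, and it is why the analysis set needs stating.

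**Conclusion.** The concern holds. The non-parametric rule contradicts the within-patient design set out in the same sentence, and nothing else in the document corrects it. The t-test branch is an omission.

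The consequence is lost power under positive within-patient correlation. On the assumptions above, for a 30% fall about half the power or more is lost from a correlation of roughly 0.5 to 0.6 upwards: at 0.50 Mann-Whitney keeps 14/34 = 41% of the signed-rank power at CV 70%, and 28/55 = 51% at CV 50%. For a 50% fall at CV 70% and correlation 0.50 it keeps 63/85 = 74%. At correlation 0 the two tests are equivalent.

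This should be corrected before analysis. An analyst who follows the text runs the wrong test, and one who departs from it makes an unplanned change.

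**What to change.** Replace the parenthesis in Statistical Analysis with wording such as:

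> paired t-test on within-patient differences (of log-transformed values for AUC and Cmax) if parametric; Wilcoxon signed-rank test on within-patient differences if non-parametric, including for Tmax; in patients with both sampling sessions

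Delete the Mann-Whitney U test. While editing, it would be sensible also to state the criterion for choosing between the branches, the scale for half-life, and how zero differences in Tmax are handled.

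The cost is one sentence. No new data, patients or procedures are needed. The LC-MS assays are run only once samples from all 10 patients are in, so the wording can be settled before any result exists.

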## **Abstract**

Morbid obesity (Body mass index > 40 kg/m^2 or 35-39 kg/m^2 with comorbidity; 37.5 kg/m^2 for Asians) is a growing global health issue. Bariatric surgery is the only intervention that has demonstrated sustainable reduction in weight and comorbidities. Among the various bariatric procedures, laparoscopic sleeve gastrectomy (LSG) has rapidly gained popularity worldwide. Physiological alterations following LSG include reduction in gastrointestinal surface and reduced retention of food. Bioavailability of drugs may be affected but published literature in this area is sparse and studies are usually small and uncontrolled. Moreover, some reports concerning gastric banding and jejunoileal bypass are no longer practiced because of the associated risk. In general, bioavailability of orally administered drug changes with a reduction in gastrointestinal area. While Kroll et al showed slight increase in area under curve of rivaroxaban post bariatric surgery, Skottheim et al demonstrated significant but variable change in systemic exposure of atorvastatin after gastric bypass (from threefold decrease to twofold increase) that diminished but was sustained with time (21-45 months post gastric bypass).

No study has investigated the change in pharmacokinetics of simvastatin post LSG.

Simvastatin is a widely-used lipid-lowering agent with a low bioavailability of 5% due to the extensive first pass metabolism. As simvastatin undergoes hydrolysis in the stomach to the active form^12, it is postulated that bioavailability of simvastatin will decrease after LSG. A decrease in bioavailability may be associated with reduced efficacy. Authors of review articles suggested choosing an alternative agent to simvastatin post bariatric surgery. However, such recommendation is largely based on theoretical concern rather than solid evidence. A previous study attempted to model the pharmacokinetics of simvastatin post Roux-en-Y and biliopancreatic diversion with duodenal switch. The data is not applicable to LSG and the model did not take into account of the pH-dependent hydrolysis. This will be the first study aiming to investigate the change in systemic exposure of simvastatin post LSG.

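### The own-control design falls back on Mann-Whitney U, an unpaired test; when the fallback is used, the pairing is lost and a real fall in exposure can be missed

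*Combined protocol and SAP*

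**What the plan says.** The Statistical Analysis section is the whole analysis plan. It states: "Each patient will serve as their own control and pharmacokinetic parameters before and after LSG will be compared with appropriate statistical tests". The tests are then named in a parenthesis: "student t-test if parametric, mann-whitney u test if non-parametric". The quantities compared are AUC, half-life, Tmax and Cmax for two analytes, simvastatin and simvastatin acid, which makes 4 × 2 = 8 comparisons.

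The design is paired throughout. Study Procedure has the same patients sampled by the same procedure before surgery and again at 3 months, and "The study aims to recruit 10 patients".

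The section names no scale, normality check, significance level, post/pre ratio, confidence interval or primary comparison. It cites a form ("See Pharmacokinetics Evaluation Form") for calculating the parameters, not for comparing them; the form is not among the documents.

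**The concern.** Mann-Whitney U treats the 10 values before surgery and the 10 after as coming from unrelated people. Differences between patients, which cancel in a paired comparison, then go into the noise. This contradicts the own-control statement in the same sentence. The t-test is not said to be paired either, although that is its likely reading. No such reading is available for Mann-Whitney U.

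The fallback could well be used: the choice depends on whether data from about 10 patients look normal, and no log transformation is planned for exposure measures.

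The stated aim is "to investigate the effect of laparoscopic sleeve gastrectomy on the pharmacokinetics of simvastatin", and the Abstract postulates a decrease. It also describes the advice to avoid simvastatin after bariatric surgery as resting mainly on theory. A non-significant result from a test that ignores the pairing could be taken as evidence against that advice when the same samples, analysed as pairs, would have shown a fall.

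**Working it through.** **The plan's own figure.** The documents give 10 patients with no effect size, variability, alpha or power, so there is no calculation to reproduce.

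**Inputs.** From the documents: 10 patients, each measured twice, and the two named tests. Assumed: all 10 complete; two-sided 0.05; lognormal exposure; true post/pre ratio 0.70, the same in every patient; within-patient CV 30%; between-patient CV 30–80%. The documents name no normality check, so Shapiro-Wilk at 0.05 on the paired differences is also an assumption.

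**Paired t-test on logs.**
- Within-patient log SD: σ = √ln(1 + 0.30²) = 0.294.
- SD of the log ratio: √2 × 0.294 = 0.415.
- Noncentrality: |ln 0.70| / (0.415/√10) = 0.357/0.131 = 2.72. With 9 df and t(0.975) = 2.262, power is 68%.
- At within-patient CV 20, 40 and 50% the same formula gives 95, 46 and 33%.

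**Other tests, by simulation** (ratio 0.70, within-patient CV 30%; power in %):

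| Between-patient CV | 30% | 50% | 60% | 80% |
|---|---|---|---|---|
| Mann-Whitney U, if used | 38 | 16 | 10 | 4 |
| Wilcoxon signed-rank on log ratios | 66 | 66 | 66 | 66 |
| Paired t, raw values | 62 | 57 | 53 | 47 |
| Trials sent to the fallback, raw values | 13 | 21 | 26 | 36 |
| Whole written rule, raw values, t-test read as paired | 60 | 50 | 44 | 35 |
| Same rule with signed-rank as fallback | 64 | 61 | 60 | 58 |

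If the analyst works on logs, the fallback is used in about 5% of trials and the whole rule keeps 65–67%.

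**Direction of the error.** With no true change, Mann-Whitney U rejects in less than 1% of trials rather than 5%. The cost is missed effects, not false positives.

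**Splitting the raw-scale loss.** At between-patient CV 80%, power goes from 68% (paired, logs) to 58% (raw rule with a paired fallback) to 35% (rule as written). About 10 points come from the raw scale and 23 from the wrong fallback. At CV 30% the steps are 68, 64 and 60%, about 4 points each.

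**Larger effect.** For a halving at within-patient CV 30%, paired log power is 99.7%, Mann-Whitney U 96–46%, and the whole rule on raw values 98.5–70%.

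**If patients differ in their true ratio.** With an assumed SD of 0.3 for the true log ratios, the SD of the observed log ratio is √(0.415² + 0.3²) = 0.512. The noncentrality is 0.357/(0.512/√10) = 2.20, and paired log power for a 30% fall is about 50%. Between-patient CV (50% in the simulated case) cancels here.

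**What an interval would show.** The 95% CI multiplies and divides the ratio by exp(2.262 × √2 × σ/√10) = 1.22, 1.35, 1.48 or 1.61 at within-patient CV 20, 30, 40 or 50%. At CV 30% an observed ratio of 0.80 has limits 0.80/1.346 = 0.59 and 0.80 × 1.346 = 1.08: not significant, yet compatible with a 41% fall.

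**The case against.** The strongest reply is that the damage may be slight. The plan fixes no scale and does not exclude logs. On logs the fallback is rarely triggered and the whole rule loses only 1–3 points against a paired t-test on logs. That stands, and it is why the loss must be given as a range.

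A reader might take 38–4% as the power of this study. It is not: it is the power of Mann-Whitney U if that test is the one used. The whole rule does better even on raw values, provided the t-test is paired.

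A reader might also infer that the t-test is unpaired, or that leaving out a ratio and interval is an error of the same kind. The documents support neither. The own-control statement makes a paired t-test the likely reading. Ratios and intervals are not ruled out, and the individual values needed for them will exist. They are a recommended addition to a very short plan for a small single-centre study.

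Nor would pairing make 10 patients enough for a moderate fall. Power is 46% at within-patient CV 40%, and about 50% at CV 30% if true ratios vary as assumed. The Abstract reports changes in atorvastatin exposure "from threefold decrease to twofold increase" after gastric bypass. That is another drug and another operation, but it is a reason not to rely on a common ratio.

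The general reference to appropriate tests does not rescue the plan, because the parenthesis then says which tests are meant.

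**Conclusion.** The contradiction is plain on the page and rests on no assumption: an own-control design is given an unpaired non-parametric test. It should be corrected.

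Its effect on the result is conditional. For a true 30% fall, under the assumptions above, the whole written rule loses between 1–3 points (logs) and over 30 points (raw values, between-patient CV 80%: 68% down to 35%). Part of the larger figure is due to the raw scale and not to the fallback. The documents give no variability with which to narrow the range, and a different normality check would move it. They do not support a claim that the study will miss a fall, nor that it risks a spurious one.

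**What to change.** **Correction.** In Statistical Analysis, replace the parenthesis naming the tests with: *paired t-test on ln-transformed AUC and Cmax; Wilcoxon signed-rank for Tmax and half-life; the test is not chosen by inspecting normality.*

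**Recommended additions, from the same data.**
- Report the post/pre geometric mean ratio with 95% CI, and the individual ratios, for simvastatin and simvastatin acid. Do not conclude absence of change from p > 0.05.
- If a session has no quantifiable drug, so that no log can be taken, list it. Compare that parameter by signed-rank on the paired differences in all patients, and still report the ratio and CI for the quantifiable pairs, labelled as incomplete.
- State one AUC window for all patients and both sessions, consistent with the Pharmacokinetics Evaluation Form. Sampling ends at 7 h, and an AUC truncated there can shift with absorption timing alone.
- Call the eight comparisons exploratory, unless one analyte's AUC is named primary before the LC-MS run.

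**Cost.** Wording only: no extra patients, samples or assays. Blood sample analysis schedules LC-MS after all patients' samples are collected, so the change can be made before any concentration is known. The downsides are that the intervals will show the limited precision of 10 patients, and that individual p-values will carry less weight.
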